9.5.2 Safety Analysis Populations

Safety analyses will be conducted in the APaT population, which consists of all randomized/allocated participants who received at least 1 dose of study treatment. Participants will be included in the treatment group corresponding to the study treatment they actually received for the analysis of safety data using the APaT population. This will be the treatment group to which they are randomized except for participants who take incorrect study treatment for the entire treatment period; such participants will be included in the treatment group corresponding to the study treatment actually received.

9.5.3 Pharmacokinetic Analysis Population

The PP population will serve as the primary population for the analysis of PK data in this study. The PP population consists of all randomized participants who receive a dose of MK-1654 and who do not have deviations from the protocol that may substantially affect the results of the PK endpoints.

The final determination on protocol deviations, and thereby the composition of the PP population, will be made prior to the final database lock.

9.5.4 Immunogenicity Analysis Population

The immunogenicity analysis populations that will be used in tertiary analyses of immunogenicity will be described in the sSAP that will be written for this study.

9.6 Statistical Methods

Statistical analyses for efficacy, safety, and PK analyses are described in Section 9.6.1, Section 9.6.2, and Section 9.6.3, respectively. No hypothesis testing for efficacy will be performed in this study. Nominal p-values may be computed for efficacy analyses but should be interpreted with caution due to potential issues of multiplicity, sample size, etc.

9.6.1 Statistical Methods for Efficacy Analyses

To estimate the efficacy of MK-1654 compared to palivizumab against RSV-associated MALRI through Day 150 post Dose 1 in RSV Season 1, efficacy is defined as:

$$E\% = 100 * \{1 - (R_t/R_p)\}$$

Where R_t and R_p are the incidence rates of RSV-associated MALRI in the MK-1654 and palivizumab groups, respectively. The incidence rate R_t is defined as $R_t = C_t/T_t$, where C_t = the count of RSV-associated MALRI cases in the MK-1654 group and T_t = total person-time of follow-up for efficacy in the MK-1654 group. The incidence rate R_p is defined similarly.

A modified Poisson regression approach with robust variance [Zou, G. 2004] will be used for the efficacy analyses. The mean and 95% CI of relative risk, R_t/R_p , will be obtained from the model, and will be used to estimate the mean and 95% CI of E. The modified Poisson regression model will include treatment group, and stratification variables of region (Southern Hemisphere and Northern Hemisphere) and participant condition (CLD, CHD, neither CLD nor CHD ≥ 29 weeks gestational age, and neither CLD nor CHD < 29 weeks gestational age) as covariates. If the number of participants in any stratum is too small and/or convergence cannot be achieved, the covariate may be excluded from the model. To allow for differences in follow-up times among the participants, the log of the follow-up time as the offset term will be added in the modified Poisson regression.

The incidence of RSV-associated hospitalization occurring from Days 1 through 150 post Dose 1 in the MK-1654 and palivizumab groups in RSV Season 1 will be estimated and the exact 95% CIs will be provided using the Chi-square distribution for Poisson variable method [Ulm, K. 1990].

An additional analysis to estimate the efficacy of MK-1654 compared to palivizumab against RSV-associated MALRI from Day 1 through the end of the first RSV season will be performed. In this analysis, only infants who develop RSV-associated MALRI from Day 1 through the end of their RSV season will be defined as cases. In other words, the efficacy follow-up duration to be included in the analysis will be until either the date of the end of the RSV season or the Day 150 date, whichever occurs first, thereby only including the relevant period of risk of RSV disease for each infant. A similar analysis will be performed for the endpoint of RSV-associated hospitalization and the incidence of this endpoint along with the CI will be estimated for each treatment group. The key efficacy analyses for secondary endpoints are summarized in [Table 6](#).

For the efficacy analyses, cases of both RSV A and RSV B associated MALRI (or hospitalization) will be counted as endpoints. The efficacy of MK-1654 relative to palivizumab in RSV Season 1 against RSV A associated MALRI and RSV B associated MALRI will also be estimated separately. Similarly, the incidence of RSV A associated hospitalization and RSV B associated hospitalization in each treatment group will be estimated separately.

The incidence of RSV-associated MALRI and RSV-associated hospitalization through Day 180 postdose MK-1654 in RSV Season 2 and the corresponding 95% CIs will be computed:

- Separately by treatment group to which participants were randomized to in RSV Season 1, and
- Both treatment groups combined.

Table 6 Analysis Strategy for Key Efficacy Variables

Endpoint/Variable (Description, Time Point)	Primary vs. Supportive Approach	Statistical Method ^a	Analysis Population	Missing Data Approach
Secondary Endpoints				
Incidence of RSV-associated outpatient and inpatient MALRI from Day 1 through Day 150 post Dose 1 in RSV Season 1	P/S	Modified Poisson regression (estimate, 95% CI)	FAS/PPE	Missing data will not be imputed
Incidence of RSV-associated hospitalization from Day 1 through Day 150 post Dose 1 in RSV Season 1	P/S	Exact 95% CIs using the Chi-square distribution for Poisson variable (estimate, 95% CI)	FAS/PPE	Missing data will not be imputed
Incidence of RSV-associated outpatient and inpatient MALRI from Day 1 through the end of RSV Season 1	S	Modified Poisson regression (estimate, 95% CI)	PPE	Missing data will not be imputed
Incidence of RSV-associated hospitalization from Day 1 through the end of RSV Season 1	S	Exact 95% CIs using the Chi-square distribution for Poisson variable (estimate, 95% CI)	PPE	Missing data will not be imputed
CI=confidence interval; FAS=full analysis set; MALRI=medically attended lower respiratory infection; P=primary approach; PPE=per-protocol efficacy; RSV=respiratory syncytial virus; S=supportive approach. ^a The statistical methods are described in Section 9.6.1.				

9.6.2 Statistical Methods for Safety Analyses

Safety and tolerability will be assessed by clinical review of all relevant parameters including AEs. All safety summaries will be provided separately for the participants' first and second

RSV seasons. Comparisons between the 2 groups will be made in RSV Season 1 only. The primary comparison of safety endpoints in RSV Season 1 will be after the first 2 doses in each group, ie, after the MK-1654 and placebo doses versus after the first 2 palivizumab doses. A supplemental comparison of safety endpoints in RSV Season 1 will be after the MK-1654 and placebo doses versus after all doses in the palivizumab group.

The analysis of safety results will follow a tiered approach (Table 7). The tiers differ with respect to the analyses that will be performed. AEs (specific terms as well as SOC terms) and events that meet PDLCS in laboratory and vital signs parameters are either prespecified as “Tier 1” endpoints or will be classified as belonging to “Tier 2” or “Tier 3” based on the observed proportions of participants with an event.

Tier 1 Events

Safety parameters or AEs of particular interest that are identified a priori constitute “Tier 1” safety endpoints that will be subject to inferential testing for statistical significance. There are no Tier 1 events for this protocol as no treatment-related SAEs have been observed in the Phase 1 studies of MK-1654.

Tier 2 Events

Tier 2 parameters will be assessed via point estimates with 95% CIs provided for differences in the proportion of participants with events (via the unstratified Miettinen and Nurminen method [1985]).

Membership in Tier 2 requires that at least 1% of the participants in any treatment group have the event. All other AEs will belong to Tier 3. Maximum body temperature will be summarized using Brighton Collaboration cutoffs.

The threshold of at least 1% was chosen to draw clinical meaningful inference. When less than 1% of participants report AEs in both groups, the 95% CI for the between-group difference may exclude zero. However, the clinical significance of these differences is unknown given the small number of participants who report AEs. Because many 95% CIs for Tier 2 events may be provided without adjustment for multiplicity, the CIs should be regarded as a helpful descriptive measure to be used in review, not a formal method for assessing the statistical significance of the between-group differences in AEs.

In addition to individual events that occur in 1% or more participants in any treatment group, the broad AE categories consisting of the proportion of participants with any AE, a drug-related AE, an SAE, an AE which is both drug-related and serious, discontinuation due to an AE, solicited injection-site AE, solicited systemic AE, solicited AE of fever measured by body temperatures, anaphylaxis/hypersensitivity AESI, rash AESI, and nonserious AE will be considered Tier 2 endpoints.

Tier 3 Events

Safety endpoints that are not Tier 1 or 2 events are considered Tier 3 events. Only point estimates by treatment group are provided for Tier 3 safety parameters.

Table 7 Analysis Strategy for Safety Parameters

Safety Tier	Safety Endpoint	95% CI for Comparison of MK-1654 and Palivizumab	Descriptive Statistics
Tier 2	Any AE ^a	X	X
	Any SAE	X	X
	Any Drug-Related AE	X	X
	Any Serious and Drug-Related AE	X	X
	Discontinuation Due to AE	X	X
	Solicited Injection-Site AEs Days 1-5 Postdose	X	X
	Solicited Daily Body Temperature Days 1-5 Postdose	X	X
	Solicited Systemic AEs Days 1-5 Postdose	X	X
	Anaphylaxis/hypersensitivity AESI Days 1-42 Post Dose 1 in RSV Season 1 ^b and 42 Days Postdose in RSV Season 2	X	X
	Rash AESI Days 1-42 Post Dose 1 in RSV Season 1 ^b and 42 Days Postdose in RSV Season 2	X	X
	Nonserious AEs Days 1-42 Post Dose 1 in RSV Season 1 ^b and 42 Days Postdose in RSV Season 2	X	X
	AEs by SOC (incidence $\geq 1\%$ of participants in one of the treatment groups)	X	X
Tier 3	AEs by SOC (incidence $< 1\%$ of participants in all of the treatment groups)		X
AE=adverse event; AESI=adverse event of special interest; CI=confidence interval; RSV=respiratory syncytial virus; SAE=serious adverse event; SOC=System Organ Class; X=results will be provided. ^a Indicates broad AE category of the number of participants reporting any AE. ^b Days 1-42 post Dose 1 in RSV Season 1 consists of safety data collected from Day 1 post Dose 1 through 14 days post Dose 2.			

9.6.3 Statistical Methods for Pharmacokinetic Analysis

Statistical methods for the PK analysis are provided below. Additional details of this analysis will be specified in a separate modeling analysis plan.

PK Analysis After Dose Administration in RSV Season 1:

Sparse PK collection is planned for the pediatric participants receiving MK-1654 in this study. Thus, population PK modeling will be used to estimate PK parameters for each participant (eg, $AUC_{0-\infty}$, C_{max} , T_{max} , $t_{1/2}$), which will be summarized in a separate population

PK modeling report. Additionally, individual concentration values for each PK sample collected will be summarized. ADA will be evaluated together with PK data to understand the effect of ADA on PK.

PK Analysis After Dose Administration in RSV Season 2:

The MK-1654 concentration after the dose given prior to the start of RSV Season 2 will be summarized by time point using descriptive statistics.

9.6.4 Demographic and Baseline Characteristics

The comparability of the treatment groups for each relevant demographic and baseline characteristic will be assessed by the use of tables and/or graphs. No statistical hypothesis tests will be performed on these characteristics. The number and percentage of participants screened and randomized and the primary reasons for screening failure and discontinuation will be displayed. Demographic variables (eg, age, gender, race, and ethnicity), baseline characteristics (including medical history as outlined in Section 8.1.4), primary and secondary diagnoses, and prior and concomitant therapies will be summarized by treatment group either by descriptive statistics or categorical tables.

9.7 Interim Analyses

An IA will occur after the first 30 participants are randomized or after the first hemisphere enrollment (~17 weeks) is complete in the initial RSV season of the study, whichever occurs first to conduct an early assessment of safety. Safety follow-up data for these participants through the RSV Season 1 Day 42 phone call will be included in this IA. Summaries of the safety, available PK data, and available incidence of RSV-associated MALRI and RSV-associated hospitalization will be reviewed by the eDMC and a recommendation on whether the study should continue will be made by the eDMC. If the study stops at the IA, no further participants will be enrolled. However, participants who have already been enrolled in the study will continue to be monitored for safety for 365 days postdose in RSV Season 1. In addition to this IA, the eDMC will review available safety and RSV disease incidence data from this study approximately every 6 months as outlined in the eDMC charter.

If the study does not stop at the IA, the study will continue until all 1000 participants have been enrolled and have completed all follow-up assessments per the protocol (365 days post Dose 1 in RSV Season 1, and 180 days postdose in RSV Season 2 [for participants receiving a RSV Season 2 dose]). At that time, a database lock will be executed. All analyses to evaluate the primary, secondary, and tertiary objectives of the study will be conducted and a CSR will be written.

If enrollment in this study is slower than expected, an IA may be performed when at least 600 participants have completed follow-up through 180 days post Dose 1 in RSV Season 1. Only data from participants who have completed the RSV Season 1 Day 60 visit and have been unblinded will be included in this IA. A database lock will be executed, and the data will be summarized and presented in a report.

The IAs will be conducted by an external unblinded statistician. Ongoing PK bioanalysis and PK modeling will be conducted by an external bioanalysis group and a separate, unblinded modeling group, respectively. Treatment-level results and/or participant-level data from the IAs will be provided by the unblinded statistician to the eDMC. The extent to which individuals are unblinded with respect to results of the IA will be documented by the unblinded statistician. The results of IA will not be shared with the investigators before the completion of the study.

The details for the reports of data reviewed by the eDMC and processes by which recommendations and decisions are reached and communicated by the eDMC will be documented in the eDMC charter for the Sponsor. The eDMC charter will be referenced in the CSR.

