9.5 Analysis Populations

9.5.1 Efficacy Analysis Populations

Full Analysis Set (FAS) Population

The FAS population will serve as the primary population for the estimation of efficacy and for the estimation of incidence of RSV-associated disease. The FAS population consists of all randomized participants who receive at least 1 dose of study treatment. Participants will be included in the treatment group corresponding to the study treatment they were randomized to for the analysis using the FAS population.

For an episode of respiratory infection to be considered for evaluation of an efficacy endpoint for the analysis in the FAS population, a PCR result from the study central laboratory must be available for an NP sample that is collected between 0 and 12 days after symptom onset and between 7 days before and 12 days after symptom worsening. A sensitivity analysis will be conducted, which will include PCR results from NP samples collected within the timeframe mentioned above but not tested at the study central laboratory.

Per-Protocol Efficacy (PPE) Population

The PPE population will serve as a supportive analysis population for the estimation of efficacy and incidence of RSV-associated disease. To be eligible for inclusion in the PPE population, study participants must satisfy the following criteria:

- Receive a complete regimen of the correct clinical material corresponding to the treatment group the participants were randomized into (ie, 1 dose of MK-1654 for participants randomized to the MK-1654 group and 3 to 5 doses of palivizumab within the protocol-specified windows for participants randomized to the palivizumab group based on the date of enrollment and the predefined RSV season end date at each site),
- Have at least 1 follow-up visit/contact for assessment of RSV disease,

- Do not undergo 1) ECMO or 2) surgical intervention for CHD requiring cardiopulmonary bypass during the efficacy follow-up period (Day 150 or Day 180), and
- At any time during dosing or efficacy follow-up, do not experience a protocol deviation that may interfere with the assessment of protection against RSV infection conferred by MK-1654.

The final determination on important protocol deviations, and thereby the composition of the PPE population, will be made prior to the final database lock and will be documented in a separate memo.

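### The optional slow-enrollment interim report keeps only infants who completed the Day 60 visit, so dosed infants who died or left before it are missing from that report

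*Combined protocol and SAP*

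**What the plan says.** Section 9.7 describes a contingent analysis for the case of slow recruitment: "an IA may be performed when at least 600 participants have completed follow-up through 180 days post Dose 1 in RSV Season 1". Its inclusion rule is "Only data from participants who have completed the RSV Season 1 Day 60 visit and have been unblinded will be included in this IA", and its output is described as follows: "A database lock will be executed, and the data will be summarized and presented in a report". Section 9.7 names no endpoints or analysis set for this report.

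The analysis populations carry no visit condition. Section 9.5.2 states: "Safety analyses will be conducted in the APaT population, which consists of all randomized/allocated participants who received at least 1 dose of study treatment". Section 9.5.1 states: "The FAS population consists of all randomized participants who receive at least 1 dose of study treatment".

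Section 9.6.2 places the main safety comparison early: "The primary comparison of safety endpoints in RSV Season 1 will be after the first 2 doses in each group".

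For the final lock, after all 1000 infants have completed follow-up, Section 9.7 states: "All analyses to evaluate the primary, secondary, and tertiary objectives of the study will be conducted and a CSR will be written".

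**The concern.** Completing the Day 60 visit is a post-randomization event, and it can depend on how the infant fared after dosing. Selecting on it removes the infants for whom early safety matters most: those who died, and those whose caregivers withdrew consent. These losses fall in the period that the primary safety comparison is built around.

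What is at stake is a locked report that shows zero deaths and zero study withdrawals before Day 60 in both arms, with nothing to tell the reader that the zeros come from the inclusion rule. Slow enrollment triggers this report, so it would circulate when the final lock is still far off. Efficacy is touched as well. The Section 9.6.1 model uses log follow-up time as an offset, so early leavers' cases and person-time are usable, but the rule discards them.

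**Working it through.** **Who is removed**

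1. Section 4.1 unblinds each infant at the Day 60 visit, and no other routine unblinding is defined. An infant who never reaches the visit fails the first condition and generally the second.
2. An infant who dies before Day 60 cannot complete the visit. Under Section 7.2, a withdrawn infant is no longer followed at scheduled visits. The early withdrawal visit in Section 8.13.4 follows Day 150 procedures, so it does not stand in for Day 60.
3. Under Sections 7.1 and 8.13.6, an infant who only stops study intervention stays in the study. That infant can complete Day 60 and be included.

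**Where the losses fall**

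The Season 1 window for adverse events of special interest closes 14 days after Dose 2. The Day 60 visit is 28 to 32 days after Dose 2. The window therefore closes at least 28 − 14 = 14 days before the visit that decides inclusion. Serious adverse events are collected beyond this, through Season 1.

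**The plan's own safety figures (Section 9.9.2)**

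Inputs: 500 infants per arm, 100% evaluable. The chance of at least one event is 1 − (1 − p)^n.

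- p = 0.33%: 1 − 0.9967^500 = 0.8085 (plan: 80%)
- p = 0.14%: 1 − 0.9986^500 = 0.5037 (plan: 50%)
- Zero-event upper bound: 1 − 0.025^(1/500) = 0.735%, or 1 in 136 (plan: below 0.74%)

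All three reproduce. They assume that every randomized infant is evaluable, which a set restricted to Day 60 attenders does not satisfy. The documents give no figures for the 600-infant report.

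**The same formula applied to the interim report**

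Assumption: 300 infants per arm (600 split 1:1). Let p be the true risk of death before Day 60, over an illustrative range.

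| True risk p | Chance of at least 1 such death in an arm of 300, all dosed infants kept | Under the rule as written |
|---|---|---|
| 0.14% | 34% | 0% |
| 0.33% | 63% | 0% |
| 1% | 95% | 0% |

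The right-hand column is zero at any risk, because such a death precludes the visit. A reader who applied the plan's zero-event bound to 0 of 300 would obtain 1 − 0.025^(1/300) = 1.22%. That reassurance would be empty, since the zero carries no information about deaths before Day 60.

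**How many infants are missing**

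Assumption: a share d of dosed infants dies or leaves before Day 60. The number removed for every 600 kept is 600/(1 − d) − 600.

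- d = 1%: 606.1 − 600 = 6.1
- d = 2%: 612.2 − 600 = 12.2
- d = 5%: 631.6 − 600 = 31.6

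These infants are additional to the 600 who trigger the analysis, because those 600 have by definition completed 180 days.

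**The case against.** The strongest reply is that the rule protects the blind. Infants still in Part 1 must not be unblinded for an interim report, and requiring a completed, unblinded Day 60 visit achieves that simply. The aim is sound and supports leaving out infants not yet due for Day 60. It does not support leaving out infants who will never reach it, and the sentence does not separate the two groups. An external unblinded statistician conducts the interim analyses, so early leavers can be counted without exposing any infant still blinded.

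The reply is also right about scope. A reader might infer that these infants vanish from the trial's primary safety results. The documents do not support that: the restriction is worded for this interim analysis only, and the final analyses use populations that keep every dosed infant. The 30-participant interim analysis and the six-monthly data monitoring reviews carry no Day 60 condition, and serious adverse events are reported to the sponsor within 24 hours. The trial tests no hypotheses, and Section 9.7 states no stopping rule tied to the 600-infant report.

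A reader might also infer that efficacy would be estimated only in infants who completed follow-up. That is not so either: those who leave after the Day 60 visit stay in.

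**Conclusion.** Wrong as written, within the optional slow-enrollment interim report only. The rule selects on a post-randomization event, conflicts with both analysis populations, and fixes the count of deaths and study withdrawals before Day 60 at zero.

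The exclusion follows from the text alone. Its numerical effect does not. The count of about 6 to 32 missing infants per 600 kept rests on an assumed 1% to 5% early loss, and the detection probabilities rest on an assumed 300 per arm. It is tempting to borrow the 10% attrition in Section 9.9.1 as the early-loss rate, but that figure belongs to the per-protocol efficacy population, where exclusions also include incomplete regimens, bypass surgery and protocol deviations.

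A reader might further infer that the report would favor one arm or understate serious events by a known amount. Without death and dropout rates before Day 60 by arm, neither the direction nor the size of such a bias can be computed.

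**What to change.** Replace the inclusion sentence in Section 9.7 with:

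> The IA includes all randomized and dosed participants (APaT for safety, FAS for efficacy) whose scheduled Day 60 visit window, counted from the Dose 1 date, closed before the data cut-off, whether or not the visit took place; participants whose window has not closed are excluded.

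Counting from Dose 1 matters because the schedule sets the Day 60 window relative to Dose 2, which an infant who left early may never have received. Do not add a separate clause admitting everyone who died or withdrew. If it reached infants whose window is still open, it would bring in recent leavers without their contemporaries who stayed, and so over-represent deaths and withdrawals. If it did not, it would be redundant.

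State also that:

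- early leavers' data are reviewed and locked before their assignment is released to the external unblinded statistician, in line with Section 9.2;
- infants still in follow-up with an overdue Day 60 visit stay blinded to the study team and sites;
- disposition before Day 60 is shown by arm.

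The cost is a short text change plus a small extra lock and code-release step for early leavers, because routine unblinding is now defined only at the Day 60 visit. No additional data collection is needed.
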